2.4.1.1 Risks of Cubii Under-Desk Elliptical

Cubii elliptical is associated with minimal risks, limited primarily to proper set-up, usage, and maintenance of the equipment. These risks include: (1) utilizing the Cubii on a non-level surface; (2) utilizing the Cubii while standing; (3) utilization of a chair with unlocked wheels; and (4) improper securing of the pedals. Prior to each study session, participant safety per the aforementioned safety checks will be assessed by the study technician.

2.4.2 Known Potential Benefits

Previous research on the use of tDCS in pwMS reported a range of immediate potential benefits such as:

- Improvement in cognitive functioning and working memory [Charvet et al., 2017]
- Reduction in depression symptoms and fatigue [Ferrucci et al., 2014; Saiote et al., 2014; Charvet et al., 2017]
- Reduction in pain and anxiety [Mori et al., 2010]

The long-term potential benefits of repeated applications of tDCS, their interaction with specific learning stages and tasks and the extent to which these performance improvements are retained in the long term remain to be addressed.

CONFIDENTIAL

This material is the property of the NYU School of Medicine and Langone Medical Center. Do not disclose or use except as authorized in writing by the study sponsor
Interventional Template Version: 28 APR 2017

The use of our established RS-tDCS protocol can improve access to physical activity programs, increase the engagement and remove the barriers of time and travel to clinic appointments (Shaw et al., 2019; Charvet et al., 2020).

3 Objectives and Purpose

In pwMS comparing those receiving active stimulation versus those receiving sham stimulation, the objectives are as follows:

3.1 Primary Objective

- To determine the efficacy and the feasibility of the combination of the tDCS and PA to improve gait performance objectively assessed using wearable inertial sensors previously validated for use in pwMS (Pau et al., 2016; 2017).

3.2 Secondary Objectives

- To determine the feasibility of delivering at-home a structured and supervised PA program paired with tDCS
- To evaluate changes in functional mobility after tDCS and PA treatment by instrumented Time Up and Go (i-TUG) performed using wearable inertial sensors at baseline, and at 4-week.
- To evaluate change in non-motor symptoms such as general perceived fatigue, cognitive and psychological aspects
- To evaluate safety and tolerability by assessing both experiences of minor adverse events and pain ratings
- To evaluate changes in level of daily physical activity and sleep as assessed by the ActiGraph device (optional)
- To collect pilot data on tDCS-related changes in brain activity as measured by 3-electrodes frontal EEG sensor (optional)
- To evaluate changes in standing balance measures provided by static Posturography test

Study Design and Endpoints

3.3 Description of Study Design

This is an interventional, randomized, double-blind (participant and study staff), sham-controlled, parallel design, pilot study of N=80 RR-MS and SP-MS participants, characterized by mild to moderate gait dysfunctions. There will be a 1:1 random assignment of participants to receive either the active or the sham tDCS while performing the PA program. Blocked stratification will be used to randomize the participants to their respective study conditions. Block sizes of 4 and 6 will be used and the stratifying factor will be EDSS score (0-3.5 and 4.0-6.5). Randomization will be done by an independent randomizer who takes no part in baseline, follow-up, or sessions to maintain the double-blind nature of the study.

3.4 Study Endpoints

3.4.1 Primary Study Endpoints

To determine the efficacy of the combination of tDCS and physical training, the following primary outcome measures have been chosen:

- Efficacy measured by comparison between the active and sham conditions by comparing the changes in gait velocity and stride length at baseline and participation end
- Compliance measured by 80% of participants having completed the study sessions

CONFIDENTIAL

This material is the property of the NYU School of Medicine and Langone Medical Center. Do not disclose or use except as authorized in writing by the study sponsor

Interventional Template Version: 28 APR 2017

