Endpoint	Primary outcome measures: 
Comparison of change in gait velocity and stride length at baseline and participation end between the active and sham conditionsThe number of participants completing the study session (goal: 80% of the participants) Secondary outcome measures: 
% of remote tDCS sessions completedComparison between the active and sham conditions on functional mobility parameters (phase duration of Sit-to-Stand, Stand-to-Sit, Mid and End turning; acceleration and angular velocity) and the Timed Up and Go Task (TUG)Comparison between the active and sham conditions on EEG signals before and after the first and final tDCS sessionComparison between the active and sham conditions on static balance abilityComparisons between the active and sham conditions on Fatigue Severity Scale (FSS), 21-item Modified form of the Fatigue Impact Scale, 12-item Multiple Sclerosis Walking Scale, Multiple Sclerosis Quality of Life-54 (MSQOL-54)
Study Duration	Estimated study start date: June 2018 Estimated study end date:

CONFIDENTIAL

This material is the property of the NYU School of Medicine and Langone Medical Center. Do not disclose or use except as authorized in writing by the study sponsor
Interventional Template Version: 28 APR 2017

[figure not shown]
Participant Duration	Approximately 6 hours to 7 hours total over 9 remote sessions plus a baseline and a follow-up visit.
Duration of IP administration	20 minutes of tDCS in each daily session
Population	Age Eligible for study: 18 years to 70 years Sex Eligible for study: All Condition: Multiple Sclerosis
Study Sites	NYU Langone Health, USA
Number of participants	80 participants
Description of Study Agent/Procedure	
Device: Active tDCS tDCS is a therapeutic treatment that utilizes low amplitude direct currents (<4 mA) to induce changes in cortical excitability. Other Name: Soterix 1x1 tDCS mini-CTDevice: Sham tDCS During a sham session, the device is programmed to ramp up to the desired intensity (target 2.5 mA) and ramp down for the initial 60 seconds, with no current delivery during the session, and then again at the end of the session. These brief periods of stimulation serve to mimic the effects of a true stimulation session.Behavioral: Physical Activity (PA) program consisting of 20 minutes of cycling on an ergonomic cross-trainer.
Reference Therapy	N/A

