7.1 Statistical Hypotheses

Research hypothesis

There is a significant difference between active and sham groups by comparing primary and secondary outcomes at baseline and end treatment time.

Null hypothesis

There will not be a significant difference between active and sham groups

CONFIDENTIAL

This material is the property of the NYU School of Medicine and Langone Medical Center. Do not disclose or use except as authorized in writing by the study sponsor

Interventional Template Version: 28 APR 2017

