7.2.2 Analysis of the Primary Efficacy Endpoint(s)

Gait speed and Stride length

- Continuous variable (repeated measure)
- The Shapiro-Wilk test will be performed: histograms will be constructed, and measures of central tendency and dispersion will be calculated to test the assumption that distribution is normal
- If normality check will fail a transformation of the data will be done as corrective procedures (transformation will be made according to data distribution)
- Repeated-measures analysis of variance (RM-ANOVA) with tDCS (2 levels: Active and Sham) as the between-independent variable and Time (3 levels: Day 1, Day 10, and After 4-weeks) as the within-independent variable. In the inferential tests statistical significance will be set at 5% and all p-values is two-sided.

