7.3 Sample Size

The sample size is calculated on the primary endpoint gait velocity measured before tDCS treatments at baseline time in a population of individuals affected by MS (0.98 ± 0.23 m/s). According to previous study the variability of changes after tDCS combined with PA is on average around 20% in active group compared with baseline assessment.

To recognize as significant change in gait velocity (alpha level = 0.05), equal to 20% difference between baseline and end of the treatment, a sample size of 19 cases for each arm will provide a power of 80%.

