Interventional Template Version: 28 APR 2017

16 Schedule of Events

Activity	Screening	Baseline	tDCS +activity sessions	Study visit 11/ Treatment End Visit (approx. 3 days after end treatment)	Follow-up visit (Optional) [4 ±1 week post- Study Visit 10]
Study team procedures					
Consent	X				
Medical History	X				
Physical Exam	X				
Height		X			
Weight		X			
Neurological examination	X				
Randomization	X				
tDCS+ PA treatment		X	X	X	
Participant device compliance check				X	
Assessment of perceived exertion (Borg Scale)			X		
Instrumented evaluation of mobility					
i-10MW test		X		X	X
Timed 25-Foot Walk (T25-FW)		X		X	X
i-TUG test		X		X	X
Static Posturography Test	X	X		X	X
EEG assessment (Optional)		X		X	
i-2MW test		X		X	X
i-DPAS (Optional)		X	X	X	X
Questionnaires, Clinical Scale and Cognitive Assessment					
BICAMS		X		X	X
Cogstate Brief Battery		X		X	X
Berg Balance Scale		X		X	X
FSS		X	X	X	X
54-MSQOL		X			X
12-MSWS		X	X	X	X
21- MFIS		X	X	X	X
VAS- F 0-10		X	X	X	X
VAS- P 0-10		X	X	X	
Reported Adverse Events		X	X	X	

CONFIDENTIAL

CONFIDENTIAL

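### Gait velocity and stride length are both primary efficacy variables, each tested at 5%, and no rule says which must succeed

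*Combined protocol and SAP*

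**What the plan says.** Three places name two primary efficacy variables. The Endpoint row of the Protocol Summary has "Comparison of change in gait velocity and stride length at baseline and participation end". Section 3.4.1 repeats it as "comparing the changes in gait velocity and stride length at baseline and participation end". Section 7.2.2 puts "Gait speed and Stride length" under the primary analysis and prescribes a repeated-measures ANOVA with arm as the between factor and three times (Day 1, Day 10, 4 weeks) as the within factor. On significance it says only: "In the inferential tests statistical significance will be set at 5% and all p-values is two-sided".

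Section 7.3 uses the singular: "The sample size is calculated on the primary endpoint gait velocity". Its target is a change "equal to 20% difference between baseline and end of the treatment". It gives a mean and SD for velocity (0.98 and 0.23 m/s) and nothing for stride length.

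Section 7.1 has one general hypothesis: "There is a significant difference between active and sham groups by comparing primary and secondary outcomes at baseline and end treatment time". It does not say whether one variable or both must differ. The primary efficacy row of the section 15 table refers only to walking abilities on the instrumented 10-metre walk, so it does not settle the matter.

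**The concern.** Two primary variables, each tested at the full 5%, need a stated rule for success. Without one, two things can go wrong.

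First, the results may disagree. If velocity reaches significance and stride length does not, or the reverse, the plan does not say whether the efficacy objective was met. The rule could then be chosen after the results are seen.

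Second, if either variable is allowed to carry the claim, the chance of at least one false difference is above the 5% set for each test.

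A related gap widens the choice. Section 7.2.2 does not say which term of the three-visit ANOVA decides. The group main effect, the group-by-time interaction and the contrast at treatment end can give different answers.

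**Working it through.** **1. The plan's own sizing, to see which endpoint it covers.** Inputs from 7.3: mean 0.98 m/s, SD 0.23 m/s, 20% change, 19 per arm, 80% power, alpha 0.05.
- Effect: 0.20 × 0.98 = 0.196 m/s; 0.196 / 0.23 = 0.85 SD. Section 7.3 words this as change from baseline; using it as a between-arm effect is an assumption.
- n per arm, two-sided 5%: 2 × [(1.960 + 0.842) × 0.23 / 0.196]² = 21.6, so 22 (23 with the t distribution). The stated 19 is not reproduced; a one-sided 5% test gives 18. That is a separate matter, and this point does not depend on it.
- With the 72 evaluable participants of section 4.5 (36 per arm), power for velocity on these inputs is 95.1% (normal approximation). No such calculation is possible for stride length from the documents.

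**2. False-positive rate under each possible rule.** Let Z1 and Z2 be the two test statistics with correlation r under no effect. The documents give no r, so a range is assumed. Section 5.2.1 takes both variables from the same walk and sensor, which makes r = 0 an upper case.
- Either suffices, either direction: 1 − P(|Z1| < 1.96 and |Z2| < 1.96). At r = 0 this is 1 − 0.95² = 9.75%.
- Either suffices, favouring active: 1 − P(Z1 < 1.96 and Z2 < 1.96). At r = 0 this is 1 − 0.975² = 4.94%. A single test has 2.5%.

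| r | Either direction | Favouring active |
|---|---|---|
| 0 | 9.75% | 4.94% |
| 0.5 | 9.07% | 4.54% |
| 0.8 | 7.81% | 3.90% |
| 0.9 | 7.04% | 3.52% |
| 0.95 | 6.46% | 3.23% |
| 0.99 | 5.66% | 2.83% |

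- Velocity alone decides: 5%.
- Both required: at most 5%.

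Using the three-visit interaction test for each variable, instead of a test on change at treatment end, gives nearly the same result: 7.9% at r = 0.8 by simulation.

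**3. Power under the candidate rules.** Inputs: 36 per arm, 0.85 SD, normal approximation.
- Velocity at the full 5%: 95.1%.
- Velocity at 2.5% (equal split): 91.5%.
- Both required: 90.5% to 93.3% for r from 0 to 0.9, if stride length has the same standardised effect, which is an assumption.

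**4. Why the deciding term matters.** Inputs: 36 per arm, a between-arm effect of 0.85 SD that persists to 4 weeks, and equal correlation between visits (assumed).
- Change from baseline to treatment end, visit correlation 0.5: the SD of change is 0.23 × √[2 × (1 − 0.5)] = 0.23, and power is 94.6% (t test).
- Group main effect: the pre-treatment visit dilutes the effect to two thirds, and power is 82.9%.
- At visit correlation 0.8: above 99.9% and 72.4% respectively.

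**The case against.** The inflation is conditional. Section 3.4.1 is one bullet joining the variables with 'and', which could mean that both must differ. Section 7.3 could mean that velocity decides. Neither reading inflates error, and no passage says that either variable suffices. This stands. A reader might infer that the trial runs at nearly twice its stated error rate; the documents do not support that, because 9.75% needs both the unwritten either-suffices rule and uncorrelated tests. What survives is that the 'and' lists what is compared and sets no success criterion, so no rule is fixed in advance.

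A reader might also infer that 7.3 flatly contradicts 3.4.1. It need not: sizing on one of two primary variables is ordinary practice, and the 7.2.2 heading allows for more than one endpoint. But 7.3 uses the singular, and a sample-size sentence is not a decision rule.

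The trial is a pilot, and completion is its other primary outcome. That lowers the weight. It does not remove the point, because section 3.1 sets an efficacy objective and 7.2.2 sets a significance level.

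Finally, the role of the 4-week visit is a separate question. The ambiguity between the two variables exists whatever is decided about that visit.

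**Conclusion.** The point holds as a missing decision rule. The firm part needs no assumption: two primary efficacy variables, each at two-sided 5%, no success rule, and no pre-set reading if they disagree.

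The numerical part is conditional. If either variable may carry the claim, the chance of at least one false difference is about 5.7% to 7.8% for an assumed correlation of 0.99 to 0.8, and 9.75% at most; about half of that favours active. If both are required or velocity alone decides, there is no inflation.

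The gap is not in the number of participants. On 7.3's velocity inputs, 36 per arm gives over 90% power under each rule checked, although for stride length this rests on an assumed equal effect. The plan should be amended; for a pilot, the stakes are moderate.

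**What to change.** 1. In the Protocol Summary, 3.4.1 and 7.2.2, name gait velocity as the primary efficacy endpoint, consistent with 7.3. State that stride length is tested at two-sided 5% only if velocity is significant. All three places must change, or the two-variable wording remains in one of them.
2. In 7.2.2, state that the deciding term is the between-arm difference in change from baseline to treatment end, not the group main effect. Sections 3.4.1 and 7.1 already frame the comparison between arms from baseline to the end, and 7.3 uses the same two time points.
3. Use one term for that time point; the Protocol Summary and 3.4.1 say participation end, whereas 7.1 and 7.3 refer to the end of treatment.

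The cost is a sentence or so in each of the three places and no added participants. Velocity keeps the full 5%. The downside is that stride length cannot support a primary claim if velocity fails. A Holm procedure or a both-required rule would also close the gap; velocity first is suggested because 7.3 already sizes on it.

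Making the 4-week visit supportive is optional and not needed here. Section 16 labels it "Follow-up visit (Optional", while section 5.3.5 lists it without that label. If the sponsor takes this step, the three-level Time wording in the Protocol Summary, 7.2.1 and 7.2.2 and the primary efficacy row of the section 15 table must be aligned. Its effect on power could go either way: under the assumptions of step 4 at visit correlation 0.5, the treatment-end contrast has 94.6%, against 96.7% for the three-visit interaction if the effect persists and 90.3% if it halves by 4 weeks.

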3.4.2 Secondary Study Endpoints

- The feasibility of delivering at-home supervised PA paired with tDCS will be assessed using the number of completed sessions at-home. It will be considered as “feasible” when participant complete successfully at least 80% of the total at-home sessions
- Comparisons between the active and sham conditions at baseline and at the end of the study by assessing the changes in gait spatial-temporal parameters (stance, swing and double support phase; cadence; step width) and functional mobility parameters objectively assessed using wearable inertial sensors
- Comparisons between the active and sham conditions at baseline and participation end conditions by assessing the changes in scores of 9-item FSS (physical aspect of fatigue) and 21-item MFIS (physical 9 items, cognitive 10 items, psychosocial 2 items), MSWS-12 (subjective measures of impact for walking ability and related pathology), and MSQOL-54 (36 items for generic health-related quality of life measures and 18 items for MS-specific measures).
- Comparisons between the active and sham conditions at baseline and participation end conditions by assessing the changes in scores of VAS- F₀₋₁₀ (to assess the perceived general fatigue)
- Review of experiences of minor adverse events and pain ratings. In particular, participants will have to report and rate any adverse events. Pain ratings will be measured, using a VAS- P₀₋₁₀ (rating 1 for minimal to 10 for most severe), before and after each session (any experience of pain or other adverse event above an intensity rating of 7 will result in study discontinuation)
- Comparisons between the active and sham conditions at pre and post tDCS-PA session by assessing the changes in the performance of the cognitive tests and EEG signal changes during the time of testing
- Comparisons between the active and sham conditions at baseline and participation end conditions by monitoring the changes in level of daily physical activity and amount of sleep as measured by ActiGraph
- Comparisons between the active and sham conditions at baseline and participation end conditions by monitoring the changes in sway parameters as objectively measured by the instrumented Posturography test and by monitoring changes in total score Berg Balance Scale.
- Change in processing speed between baseline and immediately after the treatment end to assess improvement in cognitive function as indirect effect of aerobic PA.

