4.6.2 Handling of Participant Withdrawals or Termination

If a participant wishes to withdraw from the study they may do so at any point. The participant can be contacted by e-mail, telephone or other minimum-level contact.

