5.3.4 Treatment End visit (within 3 days after session 10)

- Gait assessment with instrumented 10-meter walk (i-10MW), functional mobility assessment with instrumented Time Up and GO (i-TUG), Timed 25-Foot Walk (T25-FW), instrumented 2 minute walk (i-2MW) test, balance assessment with static posturography test, administration of Berg Balance Scale, and administration of questionnaires (9-item FSS, 21-item MFIS, MSWS-12, 54-MSQOL, and VAS- F 0-10)
- Cognitive assessment using BICAMS and CogState brief battery

5.3.5 Final Study Visit (within 4 ± 1 weeks from the end of treatment i.e. Session 10)

- Gait assessment with instrumented 10-meter walk (i-10MW), functional mobility with instrumented Time Up and GO (i-TUG), and balance assessment with static posturography test, administration of Berg Balance Scale, Timed 25-Foot Walk (T25-FW)
- Administration of questionnaires (9-item FSS, 21-item MFIS, MSWS-12, 54-MSQOL, and VAS- F 0-10)
- Record participant's adherence to treatment program
- Cognitive assessment using BICAMS and CogState brief battery
- Collect the ActiGraph device (Optional)

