5.3.6 Withdrawal/Early Termination Visit

Subjects may withdraw from the study at any time without prejudice to their care.

6 Assessment of Safety

A data safety monitoring plan (DSMP) will be implemented to ensure safety throughout the study. The study PI and Co-I [name] will be responsible for the evaluation of safety.

There is a large body of literature indicating no known safety or tolerability risk for use of tDCS. Further, tDCS is currently being studied as an alternative to relatively higher risk treatments (such as medication) in special populations such as pregnant women and developmentally disabled children. Published studies in MS, including the work in our lab here at NYULH and Stony Brook Medicine, show tDCS to be a tolerable and safe treatment approach. [name] and team at the MS Center are MS specialists with extensive experience in the assessment of patients with MS, including cognitive capacity, and including capacity to consent for numerous clinical drug trials where there is a substantially greater potential risk posed than what are the known risks for tDCS.

EEG is also established as a safe and painless procedure, with the major side-effect only being a temporary discomfort from the gel applied on the electrode patch to improve conductivity. It poses low risks even for critically ill populations as well such that it is used as a continuous monitoring tool for patients during anesthesia

CONFIDENTIAL

This material is the property of the NYU School of Medicine and Langone Medical Center. Do not disclose or use except as authorized in writing by the study sponsor

Interventional Template Version: 28 APR 2017

and in intensive care environments (Jameson, et al. 2006). Previous literature suggests that the combined use of EEG after tDCS does not increase any risks of harm. No complications or adverse events were reported for subjects whose EEG recordings were taken after performing motor tasks paired with tDCS stimulation (Polania, et al. 2012; Notturno, et al. 2013; Greecco, et al. 2014).

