6.4.4 Reporting of Pregnancy

Participants that become pregnant during the course of the study will be discontinued from treatment and will be asked to complete a concluding participation end visit that includes no risk or involvement of treatment. Only assessment will occur at the participation end visit.

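### A rating above 7 ends study participation, and the protocol does not clearly schedule an i-10MW for a participant stopped that way before session 10

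*Combined protocol and SAP*

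**What the plan says.** **The rule.** Section 3.4.2 has pain rated before and after each session and adds that "any experience of pain or other adverse event above an intensity rating of 7 will result in study discontinuation". The stated consequence is leaving the study, not leaving treatment.

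**The endpoint.** Section 3.4.1 defines primary efficacy by "comparing the changes in gait velocity and stride length at baseline and participation end". Section 7.2.2 analyses it by repeated-measures ANOVA at Day 1, Day 10 and 4 weeks.

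**The visits.**
- Section 5.3.4 is headed "Treatment End visit (within 3 days after session 10".
- Section 5.3.5 times the 4-week visit "from the end of treatment i.e. Session 10".
- Section 5.3.3, on the remote sessions, lists no walking test.
- Section 5.3.6 has a heading for a withdrawal or early termination visit. Its whole content is that "Subjects may withdraw from the study at any time without prejudice to their care".
- Section 4.6.2 says of those who leave: "The participant can be contacted by e-mail, telephone or other minimum-level contact".
- Section 16 has no early-termination column. It places the i-10MW at baseline, at the treatment-end visit and at the optional 4-week visit.

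**The contrast.** Under Section 6.4.4, participants who become pregnant "will be discontinued from treatment and will be asked to complete a concluding participation end visit", at which only assessments take place.

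**The concern.** A rating above 7 will usually come after randomisation and after stimulation has begun. If it takes the participant out of the study before session 10, the visit that supplies the primary gait value has no clear anchor for that person. Section 7.2 gives no method for missing primary values, and a standard three-time-point repeated-measures ANOVA would normally drop someone with a baseline value only.

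At the least, data are lost. If stops also fall unequally between the arms, and stopped participants would have changed differently in gait, the active-sham difference in gait speed and stride length is biased. Without a measured value, that bias can be explored only by assumption. If stops are balanced and unrelated to gait, there is no bias.

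**Working it through.** **1. Where could a stopped participant's i-10MW come from?**

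| Place in the protocol | What it offers someone stopped at, say, session 4 |
|---|---|
| 5.3.3, remote sessions | No gait test listed |
| 5.3.4, treatment-end visit | i-10MW, but timed from session 10 |
| 5.3.5, 4-week visit | i-10MW, but timed from session 10 |
| 5.3.6, early termination visit | Heading only, no assessment |
| 4.6.2, handling of withdrawals | Minimum-level contact |
| 6.4.4, pregnancy | Assessment-only end visit, for that trigger alone |
| Section 16 | i-10MW at treatment end, headed "Study visit 11/ Treatment End Visit (approx. 3 days after end treatment" |

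The grid in Section 4.4 marks a gait column at every session. That does not fit sessions 2 to 10 being remote and about 20 minutes long, the i-10MW being done in a clinical setting (5.2.1), or Section 16. The table may also have been damaged in text extraction. Even taken at face value, a session value is neither the Day 10 nor the 4-week value.

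**2. The plan's own numbers.** Section 4.5 allows 10% dropout: 80 × 0.90 = 72 evaluable, which reproduces. Section 7.3 states 19 per arm. With a difference of 0.20 × 0.98 = 0.196 m/s and SD 0.23, n = 2(z₁ + z₂)² × 0.23²/0.196². This gives 22 two-sided (23 with the t distribution) and 18 one-sided, so 19 is matched within a patient or two only one-sided. For this point it matters only that 72 evaluable exceeds all of these. On the same inputs, two-sided t-test power is 94.6% at 36 per arm and 91.9% at 32. Power is not the main issue.

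**3. How many might stop?** The documents give no rate of ratings above 7. Pain is rated 2 × 10 = 20 times per participant. Section 2.2.1 reports tolerability and feasibility above 99% over more than 2000 sessions, but with cognitive training, and that is not a rate of ratings above 7. As an assumption, let a fraction p of sessions trigger the rule, independently. The share stopped is then 1 − (1 − p)¹⁰.

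| p | Share stopped | Of 40 per arm |
|---|---|---|
| 0.1% | 1.0% | 0.4 |
| 0.25% | 2.5% | 1.0 |
| 0.5% | 4.9% | 2.0 |
| 1% | 9.6% | 3.8 (7.6 of 80) |

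Clustering of high ratings within participants would lower these figures.

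**4. What could that do to the comparison?** Let d be the excess of stops in the active arm and s the shortfall in gait change of stopped participants. Bias = s × d/40. For scale only, s is set to half or all of 0.196 m/s. Section 7.3 presents that figure as a within-active-arm change. SE = 0.23 × √(1/(40 − d) + 1/40), using the baseline SD for the SD of change (an assumption). With b = bias/SE, type I error = P(Z > 1.96 − b) + P(Z < −1.96 − b).

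| d | s (m/s) | Bias (m/s) | SE | Type I error |
|---|---|---|---|---|
| 0 | any | 0 | – | 5.0% |
| 1 | 0.098 | 0.002 | 0.0518 | 5.0% |
| 1 | 0.196 | 0.005 | 0.0518 | 5.1% |
| 4 | 0.098 | 0.010 | 0.0528 | 5.4% |
| 4 | 0.196 | 0.020 | 0.0528 | 6.6% |

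An excess in the sham arm reverses the sign. If both arms share one trigger rate, the binomial probability of an active excess of 4 or more is about 9% at p = 1% and about 0.7% at p = 0.25%.

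**The case against.** **The governing text may lie elsewhere.** Section 4.6.1 refers to explicit stop criteria in a supporting document that is not part of the supplied text, and the part of Section 5 before 5.2 is also missing from it. Either might provide a visit. This stands, and it limits the point to what the supplied sections schedule.

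**The end visit need not hang on session 10.** Section 3.4.1 speaks of participation end, Section 16 says "Study visit 11/ Treatment End Visit (approx. 3 days after end treatment", and the Section 15 table says only that measurement follows treatment end. Each could cover an early stopper. This also stands in part, but it competes with the session-10 timing in 5.3.4 and with a rule that ends study participation.

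**Stopping is discretionary elsewhere.** Sections 4.6.1 and 6.5 say that participants may be terminated or removed. Section 3.4.2 is mandatory for its own trigger, and the protocol does not reconcile the two.

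**Stronger readings to avoid.** A reader might infer that no early stopper gets a gait assessment. Section 6.4.4 contradicts that for pregnancy. A reader might also infer that active-arm participants will stop more often and bias the result. The documents do not show this. Section 2.4.1 says common adverse-effect rates did not differ between active and sham, whereas Section 6 names tingling, itching and redness as differing from sham. Background pain or hard exercise can trigger the rule in either arm. Nor is 6.6% an expected type I error. It needs a four-person excess and a purely prognostic shortfall of 0.196 m/s when tDCS has no effect, and nothing in the documents supports such a shortfall.

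**Conclusion.** The point holds in limited form. Section 3.4.2 ends study participation after a rating above 7, and the supplied visit descriptions and schedule do not clearly provide an i-10MW for someone stopped that way before session 10. Such participants may therefore lack a post-baseline value for the primary comparison.

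The certain cost, if the text is followed literally, is lost data. Bias is conditional on stops that differ by arm and relate to gait, neither of which is shown. The size is unknown and probably small: zero if stops are balanced or unrelated to gait, and a few thousandths of a metre per second for an excess of one. The larger figures rest on assumed trigger rates, an assumed shortfall and the baseline SD. The 10% dropout allowance covers numbers, not comparability between arms.

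The threshold of 7 is not challenged, and loss of complete cases through the optional 4-week visit is a separate matter. This is a cheap improvement, not a defect that undermines the trial.

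**What to change.** - **Section 3.4.2:** keep the trigger and the threshold, but make the consequence discontinuation of the tDCS and physical activity sessions, as Section 6.4.4 does for pregnancy.
- **Section 5.3.6 and Section 16:** ask stopped participants to attend the existing treatment-end assessment, with at least the i-10MW, at the originally planned date. Include the 4-week visit if it is being done. Except those who withdraw consent or for whom testing is unsafe.
- **Stop-criteria document:** bring it into line with this rule.
- **Analysis:** analyse these participants in the arm to which they were randomised, and count them as non-completers for the completion endpoint.

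This defect does not by itself require a different primary model or extra sensitivity analyses.

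**Cost:** a wording change, one column in the schedule, and up to two existing visits per stopped participant. Under the assumed rates above, that is 0 to about 8 participants of 80. No new test, equipment or staff is needed.
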